## 1. VERSION HISTORY

### 1.1 Version history of the SAP

Version Number	Summary/Reason for changes	Date issued
1.0	First version	10/06/2022

### 1.2 Version history of the Protocol

Version Number	Date	Description
1.0	06/11/2020	First version submitted

### 1.3 Version history of the eCRF

Version Number	Date	Description
1.0.0	12/03/2021	First deployment

## 2. INTRODUCTION

DermoRelizema ecofoam is a topical compact mousse indicated for treatment of the signs and symptoms associated with all types of dermatitis (including atopic, contact dermatitis, dermatitis caused by radiotherapy and by sun radiations) and erythema. The mechanism of action of DermoRelizema ecofoam is based on the creation of a protective thin layer on the skin, which protects the skin against external irritants without hindering normal transpiration. It helps reducing skin redness and its derma-protective action it helps maintaining and restoring the physiological skin barrier. Thanks to its light texture, it can be easily applied on wide areas.

DermoRelizema ecofoam is a CE marked medical device class IIa, manufactured by Relife Srl, that is the Sponsor of this post-market clinical follow-up investigation.

In this clinical investigation DermoRelizema ecofoam will be used to treat and alleviate dermatitis severity and symptoms as perceived by the patients, in compliance with its Instructions for Use (IFU). Different typologies of skin conditions will be treated like atopic dermatitis, irritant dermatitis, contact dermatitis, as they have common symptomatology and they all could benefit from the treatment with the topic product under investigation.

Dermatitis is a skin inflammatory disease commonly spreading in a limited area of the body and characterized by reddening, itching and skin dryness of the affected epidermis. Dermatitis is a condition that can interfere with social function, sleep and employment. Its persistence and accompanying pruritus may be stressful and frustrating for patients.

The most common types of dermatitis are contact dermatitis (CD) and atopic dermatitis (AD), also referred as atopic eczema, but also dermatitis caused by radiotherapy or solar radiations can occur. Only atopic dermatitis and contact dermatitis will be included in this clinical investigation.

DermoRelizema ecofoam (DLP034) CE mark was supported by literature research. In order to allow the Manufacturer, Relife Srl, to review and confirm the clinical performance and safety of the medical device DermoRelizema ecofoam in the post-market phase, this post-market clinical follow-up investigation was designed and is going to be conducted in adult males and females affected by mild to moderate dermatoses, like AD, ICD or ACD.

### **3. STUDY OBJECTIVES**

#### **3.1 Primary Objective**

The primary objective of this clinical investigation is to evaluate and confirm the performance of the DermoRelizema ecofoam medical device in the improvement of the dermatitis severity, by alleviating the symptomatology.

The disease severity was clinically measured through the Investigator Global Assessment (IGA) for dermatitis after 28 days of treatment.

#### **3.2 Secondary Objectives**

The secondary objectives of this clinical investigation are:

1. to evaluate the performance of DermoRelizema ecofoam in the improvement of dermatitis severity (IGA) after 14 and 42 days of treatment;
2. to evaluate the eczema improvement through the EASI (Eczema Area and Severity Index) score;
3. to evaluate the improvement in itching, burning, pain and pruritus at visits, as reported by the subject at visits by VAS;
4. to evaluate improvement in the Quality of Life (QoL) of the subject related to his/her dermatitis, through the DLQI (Dermatology Life Quality Index) questionnaire;
5. to evaluate the subject's adherence to treatment.
6. to evaluate the subject's and Investigator's global evaluation of performance of DermoRelizema ecofoam;
7. to evaluate the subject's overall acceptability of DermoRelizema ecofoam.

### **4. STUDY METHODS**

#### **4.1 Study Design**

This is a multicenter, open label, uncontrolled, post-market clinical follow-up investigation.

All the subjects were allocated to the following treatment group:

- DermoRelizema ecofoam, topically applied twice a day in all the affected areas for 42 consecutive days.

The subject started treatment on the first day of study and continued until 42 days after the first application. The treatment may have been prolonged or shortened of maximum 2 days, in the case intermediate and/or final visits were delayed.

#### **4.2 Treatment Administration**

Patients were instructed to use DermoRelizema ecofoam two times daily: the first application in the morning and the second in the evening before bedtime, for 42 consecutive days.

At the first use of the product the patient were instructed to press the valve two or three times to activate the pump mechanism. After this, the subject pressed the valve gently to obtain one or more doses of the product to apply on the selected area and massage.

#### **4.3 Randomization and Blinding**

Not applicable: open-label clinical investigation.

### **5. STUDY ENDPOINTS**

#### **5.1 Primary Endpoint**

Change from baseline (Visit 1) to day 28 (Visit 3) in Investigator Global Assessment (IGA). The assessment will be also dichotomized in terms of treatment success or treatment failure.

#### **5.2 Secondary Endpoints**

Secondary endpoints are:

1. Change from baseline (Visit 1) to day 14 (Visit 2) and day 42 (Visit 4) in Investigator Global Assessment (IGA). The assessment will be also dichotomized in terms of treatment success or treatment failure and described using Number (N) and the proportion of patient (%).
2. Change from baseline (Visit 1) to each time point (day 14, day 28 and day 42) in EASI (Eczema Area and Severity Index) score.
3. Change from baseline (Visit 1) to each time point (day 14, day 28 and day 42) in DLQI (Dermatology Life Quality Index) score.
4. Change from baseline (Visit 1) to each time point (day 14, day 28 and day 42) in itching, burning, pain and pruritus, as reported by the subject by VAS.
5. The subject's adherence to treatment (number of applications reported on the subject's diary).
6. The subject's and Investigator's global evaluation of performance of DermoRelizema ecofoam, through a specific questionnaire. The variable will be also dichotomized in terms of improved/not improved.
7. To evaluate the subject's overall acceptability of DermoRelizema ecofoam, through a specific questionnaire.

#### **5.3 Safety Endpoints**

To evaluate the local and general tolerability of DermoRelizema ecofoam. Adverse events and adverse device events were recorded and evaluated.

### **6. PLANNED ANALYSIS**

#### **6.1 Interim Analysis**

No interim analysis is planned.

## 6.2 Final Analysis

Final analysis will be performed according to the protocol and to this Statistical Analysis Plan, after data cleaning operations and DB Lock will be performed. The statistical analysis will be performed using SAS 9.4 for Windows (SAS Institute Inc., Cary, NC, USA).

## 7. SAMPLE SIZE AND STATISTICAL POWER CONSIDERATION

An exact binomial test with a nominal 5% two-sided significance level has 80% power to detect the difference between the Null hypothesis proportion,  $\pi_0$  of 0.5 (i.e., 50% of patients with treatment success) and the alternative proportion,  $\pi_1$ , of 0.75 (i.e., 75% of patients with treatment success) when the sample size is 30 subjects. Assuming a possible 25% dropout rate, 40 subjects were enrolled, according to the CIP provisions.

## 8. ANALYSIS POPULATIONS

### 8.1 Full Analysis Set (FAS)

The FAS population includes all subjects of the safety population who have performed the baseline assessments and had at least one post-baseline assessment of any performance endpoint (primary or secondary).

### 8.2 Per-Protocol (PP) Population

The PP population includes all subjects of the FAS who also met all inclusion/exclusion criteria and who did not have any major protocol deviation.

### 8.3 Safety Population

The Safety Population includes all the subjects enrolled who signed informed consent and received at least one administration of the investigational device.

## 9. GENERAL ISSUES FOR STATISTICAL ANALYSIS

### 9.1 Definitions, Derived Variables and Datasets

Variable	Type	Description
qsorres_iga	Discrete	Investigator's global assessment: 0 = Clear 1 = Almost clear 2 = Mild 3 = Moderate 4 = Severe 5 = Very severe
qsorres_easi	Continuous	EASI Score
qsorres_dlqi	Continuous	DLQI score
qsorres_vas_pain	Continuous	VAS for pain rating

qsorres_vas_itch	Continuous	VAS for itching rating
qsorres_vas_burn	Continuous	VAS for burning rating
qsorres_vas_prur	Continuous	VAS for pruritus rating
ecdos_skipped	Continuous	Treatment skipped applications
ecdosfrq	Continuous	Treatment performed applications
qsorres_su_perf	Discrete	Subject's global evaluation of performance: 1 = Very much improved 2 = Improved 3 = Minimally improved 4 = No change 5 = Minimally worse 6 = Worse 7 = Very much worse
qsorres_inv_perf	Discrete	Investigator's global evaluation of performance: 1 = Very much improved 2 = Improved 3 = Minimally improved 4 = No change 5 = Minimally worse 6 = Worse 7 = Very much worse
qsorres_su_sat	Discrete	Subject's overall acceptability – Pleasant feeling with product: 1 = Very much satisfied 2 = Satisfied 3 = Neither satisfied nor dissatisfied 4 = Dissatisfied 5 = Very much dissatisfied

### 9.1.1 Baseline Values

Data and Measures collected at Visit 1, before any study treatment administration, are considered as baseline values.

### 9.1.2 Duration of Exposure

The planned treatment duration was of 1,5 month (42 days  $\pm 2$ ).

### 9.1.3 Treatment Compliance

The Investigator was responsible for ensuring the accountability of the study product.

The Investigator should maintain records that adequately documented:

- that the subjects were provided with the quantities specified by the clinical investigation plan/amendment(s)
- that all study products provided by the Sponsor were fully reconciled.

The investigator visually checked the empty/unused/partially used tubes of study product returned by the subjects at study visit. In order to quantify the compliance to the treatment the Investigator also asked to the subject if the product was used according to the instructions, how many times the treatment was skipped and how many study product applications were performed, according to subject's diary. The subject will be considered compliant to the treatment if the number of skipped applications is not exceeding 20% of the expected applications (i.e. the compliance of a compliant subject should be between 80% e 120%).

In the Listing 16.2.5, adherence to treatment will be described.

#### **9.1.4 Methods for Withdrawals and Missing Data**

Missing data will not be replaced in any statistical analysis.

#### **9.2 Multicenter Studies Considerations**

No covariates or interaction analysis will be performed.

#### **9.3 Multiple Comparisons and Multiplicity**

This is a single-arm clinical investigation and no adjustment for multiplicity will be used.

#### **9.4 Data Safety Monitoring Board (DSMB)**

No DSMB was established for this study.

### **10. STUDY SUBJECTS**

#### **10.1 Disposition of Subjects**

Subjects' disposition by study visit will be described and summarized in the Table 14.1.1. Reasons for withdrawal will be described.

#### **10.2 Protocol Deviations**

Protocol deviations will be reviewed and discussed with the sponsor before the database lock during Data Review Meeting.

Protocol deviations will be summarized in the Table 14.1.2 and described in the Listing 16.2.2.

### **11. EFFICACY ANALYSIS**

#### **11.1 Analysis datasets**

The analysis of safety endpoints will be performed on the Safety population. Analysis of performance endpoints will be performed on the FAS population. The analysis of primary endpoint will be repeated in the Per-Protocol population.

## 11.2 Demographics and Baseline Characteristics

Demographic (gender, age) and baseline characteristics will be summarized in the Tables 14.1.3 and 14.1.4. Medical history and surgical history will be summarized in the Tables 14.1.5 and 14.1.6.

From Listing 16.2.4.1 to Listing 16.2.4.4, all demographic and baseline characteristics will be described.

The descriptive statistics will include number of observations, mean, standard deviation, median, minimum and maximum for continuous variables and number of observations and their percentages for categorical parameters.

## 11.3 Measurements of Treatment Compliance

Treatment compliance will be assessed through the counting of the number of performed applications, according to the subject's diary and through the counting of the number of planned applications.

The number of performed applications will be recorded on the eCRF separately for the three study periods: Visit 1 – Visit 2, Visit 2 – Visit 3 and Visit 3 – Visit 4. The total number of performed applications will be the sum of the performed applications of the three study periods. The total number of planned applications will be estimated based on the treatment duration x 2 times.

To calculate the treatment compliance, the following formula will be used:

$$\frac{\text{Total number of performed applications}}{\text{Total number of planned applications}} * 100$$

Treatment compliance will be described in Listing 16.2.5.

## 11.4 Efficacy Analysis

### 11.4.1 Primary Efficacy Endpoints

Wilcoxon signed-rank test will be used to assess a significant change in Investigator Global Assessment (IGA) from baseline (Visit 1) to day 28 (Visit 3). The assessment will be also dichotomized in terms of treatment success (decrease in IGA between baseline and day 28  $\geq 1$ ) or treatment failure (no decrease in IGA, i.e. IGA at day 28 equal to or higher than IGA at baseline). It will be described using number (N) and the proportion of subjects (%) in the Tables 14.2.1.1 and 14.2.1.2. The proportion of treatment successes will be compared to a referent proportion (50%, Null hypothesis proportion) using the exact binomial test.

### 11.4.2 Secondary Efficacy Endpoints

Wilcoxon signed-rank test will be used to assess a significant change in Investigator Global Assessment (IGA) from baseline (Visit 1) to day 14 (Visit 2) and day 42 (Visit 4). The assessment will be also dichotomized in terms of treatment success (score decrease  $\geq 1$ ) or treatment failure (no score decrease). It will be described using number (N) and the proportion of subjects (%). The proportion of treatment successes will be compared to a referent proportion (50%, Null hypothesis proportion) using the exact binomial test.

Changes from baseline (Visit 1) to 14 days (Visit 2), 28 days (Visit 3) and 42 days (Visit 4) of treatment in EASI score, DLQI score and VAS for pruritus, itching, burning and pain severity will be analyzed using paired Student's t-test (or Wilcoxon signed-rank test if the variable is not normally distributed).

The number of applications reported on the subject's diary will be used to evaluate adherence to treatment. Treatment compliance will be summarized by the number of patients (N), mean, standard deviation, median, minimum, maximum.

Subject's and Investigator's global evaluation of performance of the study product obtained at the end of the study (Visit 4) by means of a 7-items scale will be summarized through number (N) and proportion of subjects (%) for each item. The variable will be also dichotomized in terms of improved (1=Very much improved or 2=Improved or 3=Minimally improved) or not improved (4=No change or 5=Minimally worse or 6=Worse or 7=Very much worse).

Subject's evaluation of overall acceptability with treatment, obtained by means of a 5-item scale will be summarized through number (N) and the proportion of subjects (%) for each item.

The secondary endpoints will be described from Table 14.2.2.1 to Table 14.2.2.8.

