#### 7.3.5.2 Secondary endpoints

Wilcoxon signed rank-sum test will be used to assess significant changes in IGA from baseline to day 14 and 42. IGA will be also dichotomized in terms of treatment success (score decrease  $\geq 1$ ) or treatment failure (no score decrease) and described using number (N) and the proportion of patients (%).

Changes from baseline (Visit 1) to 14 days (Visit 2), 28 days (Visit 3) and 42 days (Visit 4) of treatment in EASI score, DLQI questionnaire and VAS for pruritus, itching, burning and pain severity will be analyzed using paired t-test.

The number of applications reported on the subject's diary will be summarized to evaluate adherence to treatment.

Subject's and Investigator's global evaluation on performance of the study product performed at the end of the study (Visit 4), by means of a 7-items scale, will be summarized through number (N) and proportion of patients (%) for each item. The variable will be also dichotomized in terms of improved/not improved.

Subject's evaluation of overall acceptability with treatment, performed by means of a 5-item scale will be summarized through number (N) and proportion of patients (%) for each item.

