### 16.1 *Study Discontinuation*

Subjects may be discontinued at any time from the study for any of the following reasons:

- An AE occurs that, in the opinion of the Investigator, makes it unsafe for the subject to continue in the study
- Lack of compliance of the subject to the study treatment or assessments
- The subject needs to use a medication/treatment not allowed for a disease or for a flare of the dermatitis
- The subject is lost to follow-up
- The subject dies
- The subject withdraws consent
- The Investigator, for any reason, terminates the entire study, or terminates the study for that subject or the attending physician requests that the subject be withdrawn for any medical reason

- The Sponsor or the Regulatory Authority or the Ethics Committee, for any reason, terminates the entire study or terminates the study for this site or for a particular subject.

If a subject is discontinued from the study, the Investigator will, as far as possible, complete the end of study visit (Visit 4) e-CRF fields. The Investigator should try to ascertain the reason(s) for withdrawal, while fully respecting the subject's rights.

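### EASI, DLQI and VAS are tested on observed pairs although subjects may be discontinued for flare treatment: Day 28 can lean toward improvement, and Day 42 depends on an unstated rule for early-termination values

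*SAP*

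**What the plan says.** Protocol 7.3.5.2 says that changes from Visit 1 to each later visit in EASI, DLQI and the VAS for pruritus, itching, burning and pain "will be analyzed using paired t-test". SAP 11.4.2 has the same comparisons, which "will be analyzed using paired Student's t-test (or Wilcoxon signed-rank test if the variable is not normally distributed". Six scores at three visits make 18 separate tests.

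On the data that enter them, SAP 11.1 says "Analysis of performance endpoints will be performed on the FAS population" and SAP 9.1.4 says "Missing data will not be replaced in any statistical analysis". One post-baseline assessment of any performance endpoint is enough to enter the FAS (SAP 8.1). No repeated-measures model, imputation or sensitivity analysis is planned for these scores.

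Among the reasons for which a subject may be discontinued, Protocol 16.1 lists: "The subject needs to use a medication/treatment not allowed for a disease or for a flare of the dermatitis". The same section asks the investigator to complete the Visit 4 e-CRF fields for a discontinued subject as far as possible. Table 1 (Study Flow-Chart) marks Visit 4 as also being the early termination visit. The SAP does not say whether a value collected that way counts as a Day 42 value.

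**The concern.** A paired test uses only subjects who have both the baseline value and the value at that visit. The set labelled FAS therefore becomes, at each later visit, the subset still under observation. If those who leave tend to be doing badly, the remaining mean change is too favourable, and with no control arm nothing offsets this.

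Day 28 is the most exposed visit. Someone who leaves between Visits 2 and 3 has a Day 14 value and perhaps an early-termination value in the Visit 4 fields, but nothing at Visit 3. The paired test at Day 28 ignores the Day 14 value, although it carries information about the missing one.

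At stake are the symptom, eczema-score and quality-of-life results. The primary IGA test is a separate analysis.

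**Working it through.** **The plan's own figure.** SAP 7 states: "An exact binomial test with a nominal 5% two-sided significance level has 80% power", with a null "of 0.5 (i.e., 50% of patients with treatment success" and an alternative "of 0.75 (i.e., 75% of patients with treatment success", for 30 subjects. For X ~ Bin(30, p), declare success at X ≥ 21. Then P(X ≥ 21 | 0.5) = 0.0214 (two-sided 0.0428) and P(X ≥ 21 | 0.75) = 0.803. Enrolment is 30 / (1 − 0.25) = 40. Both reproduce. They concern IGA success only; no figure is stated for EASI, DLQI or VAS.

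**Inputs.**
- From the documents: 40 subjects, a 25% dropout allowance (10 subjects), no replacement, visits at Days 14, 28 and 42.
- Assumed, because the documents give none: unit SD at every visit, equal correlation ρ of 0.4 or 0.6 between visits, and no true change. Dropout after Visit 2 takes the f × 40 subjects with the highest dropout score, which has correlation m with the Day 14 change. m = 1 means that exactly the worst responders leave; m = 0.5 is a moderate relation. Negative change is improvement.

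**Day 28 bias on observed pairs.**
- SD of a change: √(2(1 − ρ)) = 0.894 at ρ = 0.6 and 1.095 at ρ = 0.4.
- Correlation of the Day 14 and Day 28 changes, which share a baseline: (1 − ρ) / (2(1 − ρ)) = 0.5.
- Mean dropout score of those who stay, with z the upper-f normal quantile: −φ(z) / (1 − f). This is −0.103/0.95 = −0.109 for f = 0.05, −0.175/0.90 = −0.195 for f = 0.10, and −0.318/0.75 = −0.424 for f = 0.25.
- Bias = −m × 0.5 × φ(z)/(1 − f) × SD of change. For 10 losses at m = 1: 0.5 × 0.424 × 0.894 = 0.19, and 0.5 × 0.424 × 1.095 = 0.23.

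| Leave | m | Bias, ρ = 0.6 | Bias, ρ = 0.4 | Simulated false improvement (nominal 2.5%) |
|---|---|---|---|---|
| 2 | 1 | −0.05 | −0.06 | about 5% |
| 4 | 1 | −0.09 | −0.11 | 8–9% |
| 10 | 1 | −0.19 | −0.23 | about 22% |
| 2 to 10 | 0.5 | −0.02 to −0.10 | −0.03 to −0.12 | about 4–8% |

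The formula is for large samples. Simulation with 40 subjects gives slightly smaller biases: −0.02 to −0.11 SD in the milder rows and −0.18 to −0.23 SD in the third. With dropout unrelated to outcome, the rate stays at 2–3%.

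**Day 42.**
- Early-termination values missing or unused: under equal correlation the formula is unchanged, so the bias is as at Day 28.
- Early-termination values analysed as Visit 4, taking the value at withdrawal to be the Day 14 change: a fraction f contributes the full deviation instead of the half expected by Day 42. The bias is f × 0.5 × (φ(z)/f) × SD = 0.5 × 0.318 × 0.894 = +0.14 at ρ = 0.6, and 0.5 × 0.318 × 1.095 = +0.17 at ρ = 0.4. Simulated false improvement is about 0.1%.

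**What a likelihood analysis using all visits recovers at Day 28** (ρ = 0.6, m = 0.8):
- Dropout driven by the recorded Day 14 change: observed pairs −0.07 SD (10% dropout) and −0.15 SD (25%); likelihood estimate about 0.00 in both.
- Dropout driven by the unrecorded Day 28 change: observed pairs −0.14 and −0.30 SD; likelihood estimate −0.10 and −0.22 SD.

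At ρ = 0.6 with the 10 worst Day 14 responders lost, the standard error at Day 42 is 0.18 SD for the likelihood estimate against 0.16 SD for observed pairs.

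**The case against.** The case on the other side is substantial.

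- A reader might infer that every subject who flares is withdrawn. Protocol 16.1 is permissive, and the listed reason is needing a non-permitted treatment. It stands among others, such as withdrawal of consent and loss to follow-up, that need not follow response.
- A reader might infer that Day 42 is also biased toward improvement. The documents do not support that, because Visit 4 doubles as the early termination visit. Used as Day 42 values, those assessments reverse the bias. What remains is a missing rule.
- The 22% figure assigns the whole dropout allowance to exactly the 10 worst Day 14 responders. The 25% is a planning allowance, and no flare rate is given. The rate also assumes no true change; where improvement is real, the same bias exaggerates it and does not create it.
- Losses are not hidden. The missing-data rule is stated, the mock table (SAP 14.4.2) prints N at each visit, and disposition with reasons for withdrawal is reported (SAP 10.1). This shows the loss but corrects neither the estimate nor the p-value.
- These are secondary, unadjusted tests with no power statement, in an uncontrolled post-market study. That limits the weight of the point. It does not remove the Day 28 mechanism.

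**Conclusion.** The point holds at Day 28: observed-pair tests without replacement, a discontinuation reason linked to outcome, and early-termination data that leave Visit 3 empty can together bias the result toward improvement. At Day 42 the direction is open until the SAP says how early-termination values are used.

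Under the stated assumptions the Day 28 bias is about 0.02 to 0.11 SD, with 4–9% false improvement, for 2–4 strongly response-related losses or 2–10 moderately related ones. About 0.2 SD and 22% is the extreme of that set. If flares arise between visits and dropout follows a value never recorded, the bias can be larger, as the last part of the working shows. All sizes rest on assumed SD, correlation and dropout mechanism; the documents establish the mechanism, not its size.

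This is a worthwhile, inexpensive improvement to the secondary analyses. It is not evidence that their results will be wrong.

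**What to change.** Keep the paired tests and add one paragraph to SAP 11.4.2 and 9.1.4 before database lock:

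- As a sensitivity analysis, fit a mixed model for repeated measures to EASI, DLQI and each VAS, with baseline and all visits as outcomes, visit as a factor, unstructured covariance and all FAS subjects. Report mean change and 95% CI at Days 14, 28 and 42.
- Assign early-termination values to the scheduled visit nearest the actual assessment day, not automatically to Day 42, and say which value counts if that visit already has one.
- Report the number of flare-related withdrawals beside each result.
- If the paired and model-based results disagree, say so in the conclusion.

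The cost is that paragraph and a short SAS PROC MIXED program on data already collected at every visit. The downsides are slightly wider intervals, a normality assumption for bounded scores, and only partial removal of bias if dropout depends on values never recorded. For these reasons the model is added to the paired tests and does not replace them.
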